10.2.4 EGFR Mutation Test at Screening

Tumor tissue samples for the test can be derived from primary tumors or from metastatic tumors.

Tumor biopsy samples for screening should not be collected from tumor lesions after local treatment such as irradiation. Biopsy samples are not limited to the 28-day screening timeframe. If the biopsy sample is collected from tumor tissue that has disease progression to stage IIIB or IV, a repeat biopsy will not be required.

A patient who fails screening for the first tumor tissue test may be re-screened if it is considered by the Investigator to be possibly related to sample collection, and the patient needs to re-sign the ICF before re-screening. Repeated testing will not be required if the laboratory test and imaging examination are within the timeframe at the time of re-screening, and re-testing will be required if the timeframe is exceeded.

When blood samples are submitted, if the test result is negative for EGFR mutation, a tumor tissue sample will be recommended for the second test.

10.2.5 Genetic Testing after Disease Progression

If a subject has disease progression, tumor tissue and/or blood samples will be collected (tumor tissue samples are recommended) based on the subject's willingness. For patients treated with HS-10296, post-disease genetic testing for progression will be performed using next-generation sequencing technology to guide further treatments.

The requirements for sample collection are shown in the following table, and the collected samples are shipped to Beijing Gene Plus Clinical Laboratory Co., Ltd., as required for gene testing, including the following genes: EGFR, ALK, ROS1, RET, MET, NTRK, TP53, BRAF, KRAS, NRAS, PI3K, and HER2.

Sample Type	Requirements for Samples	Sample Storage	Sample Shipment
Fresh tissue	1. Surgically resected tissue: ≥ 60 mg, approximately soybean-sized 2. Needle aspiration of tissue: ≥ 1 needle, sample diameter of 1-2 mm, longer than 0.5 cm	Stored at normal temperature (0-37°C) in tissue preservation tubes	Shipment at 0-37°C
Formalin-fixed paraffin-embedded tissue	1. Paraffin block: 1 piece 2. Paraffin section: 10 pieces (3-5 μ m)	Stored at normal temperature (0-37°C) in slide storage boxes	Shipment at 0-37°C
Peripheral blood	10 mL Sterck peripheral blood	Temporarily stored at 6-37°C, and refrigeration is prohibited	Shipment at 6-37°C

10.3 Safety Evaluation

Occurrence of adverse events; occurrence of serious adverse events; proportion of patients withdrawing due to adverse events; laboratory changes (blood chemistry, hematology, and urinalysis); changes in vital signs, physical examination, body weight, ECG, LVEF, ECOG performance status score, and ophthalmic examination.

10.4 Management of Biological Samples

10.4.1 Blood Collection Volume

The sampling volume from the start of the screening period to Cycle 7 (18 weeks) will be 150 mL according to the study plan (Table 4).

Table 4 Vol. of blood to be collected

Visit	Safety (mL) ^a
Screening period	15
C1	45
C2	15
C3	15
C4	15
C5	15
C6	15
C7	15

Total	150
--------------	------------

Note: ^a 6 mL for blood chemistry analysis and 9 mL for hematology analysis.

The total sample size required may be adjusted according to the specific procedures and changes in the protocol and the method established by the central laboratory.

The safety laboratory assessments will be performed at each study site's laboratory according to their established methods. Therefore, the total sample size required may vary from site to site.

10.4.2 Destruction of Biological Samples

Biological samples will be stored for a maximum of 15 years from the date of the last visit of the last patient (LPLV), after which they will be destroyed.

10.4.3 Labeling and Supervision of Biological Samples

Samples collected for purposes other than clinical testing will be identified by study number and patient's screening number to ensure that the data can be associated with clinical data. Samples may be destroyed in the event that the patient withdraws his/her consent, and may be subject to regulatory review.

11.0 Adverse Event and Medical Management

11.1 Adverse Event

11.1.1 Definition of Adverse Events

An adverse event (AE) is an unexpected medical condition or worsening of a pre-existing medical condition after or during exposure to the investigational product, regardless of their causal relationship to the investigational product. Unexpected medical conditions may be symptoms (e.g., nausea, chest pain), signs (e.g., tachycardia, liver enlargement), or abnormal findings from tests (e.g., laboratory tests, ECGs).

Aggravation of the disease under investigation and its associated symptoms or signs will not be considered as AEs, if they are expectable judged by the investigator.

11.1.2 Definition of Serious Adverse Events

A serious adverse event (SAE) is defined as an AE that occurs during the study and meets one or more of the following criteria:

- Leading to death
- Immediately life-threatening
- Requiring inpatient hospitalization or prolongation of existing hospitalization
- Results in permanent or significant disability/incapacity to work or substantial disruption of the ability to conduct normal life functions

- Results in a congenital anomaly/birth defect
- Is a significant medical event that may jeopardize patients' safety or may require medical intervention to prevent one of the outcomes listed above

11.1.3 Recording of Adverse Events

11.1.3.1 Time Period for Collecting AEs and SAEs

AEs will be collected throughout the study from informed consent to the end of the safety follow-up period. The safety follow-up period is defined as 28 days after discontinuation of the investigational product.

SAEs occurring throughout the study (from informed consent to the end of the follow-up period) should be reported to the Sponsor by the site within 24 hours of becoming aware of the SAEs.

After discontinuation of HS-10296, SAEs considered related to the investigational product and study procedures should be continued collecting, and the patient's disease progression should be followed. Some patients may remain on medication after the last database lock. For patients who continue receiving HS-10296, the Sponsor will collect only SAEs, as well as information on discontinuation of study treatment due to AEs/SAEs, until 28 days after discontinuation of treatment.

11.1.3.2 Follow-up of Unresolved Adverse Events

At the patient's last study visit, any medically indicated unresolved AE will be followed by the investigator, but the information will not need to be further recorded in the eCRF. If necessary, the investigator will reserve the right to collect information related to ongoing AEs after the end of the study. If the investigator becomes aware of any new onset of SAEs at any time after the patient has completed the study and the investigator considers the event possibly related to HS-10296, the investigator should notify the Sponsor within 24 hours after the awareness of the SAEs.

11.1.3.3 Key Information of Adverse Events to be Collected

The key information collected for each AE will include, but is not limited to the following:

- Diagnosis/description of AE
- Start date and end date of AE
- Maximum CTCAE grade
- Whether the AE is serious or not
- Investigator's assessment of causality
- Treatment of the event (drug therapy and non-drug therapy)

- Outcome

For SAEs, the following information will be collected:

- Event name (diagnosis)
- Description of the event
- Severity of the event
- Start date and end date of event onset
- Any relevant medical history, concomitant medications/therapies and laboratory results
- Treatment of the event (drug therapy and non-drug therapy)
- Investigator's assessment of causality
- Cause of death (if it is a death event)

All AEs will be graded by Common Terminology Criteria for Adverse Event (CTCAE) as per the grading criteria in CTCAE Version 4. For AEs that are not graded by CTCAE, the recommendation in the CTCAE criteria should be used to convert mild, moderate, and serious events to CTCAE grades.

11.1.4 Causality Assessment

The investigator will assess the causality of the investigational product and each AE. Criteria for judging the relationship of AEs and the investigational product are shown in Table 5.

Table 5 Judgment Criteria for Relationship of Adverse Events and the Investigational Product

Grade	Judgment criteria
Definitely unrelated	The adverse event is not related to the use of the investigational product. For example: no investigational product is used.
Unlikely related	There is no evidence of a causality between the event and the investigational product. The onset of an AE is more likely to be related to other factors, such as concomitant medications or concomitant diseases. However, a correlation cannot be ruled out.
Possibly related	The onset of an AE shows a reasonable chronological order with the use of the investigational product, and the onset of the AE may be caused by the investigational product. Whether it may be caused by other factors cannot be ruled out, such as: concomitant medications or concomitant diseases. No withdrawal or the information is unknown.
Definitely related	The type of AEs has been identified as a known type of reaction to the drug and cannot be explained by other reasons (e.g., concomitant medications and concomitant diseases). The time to onset of the event strongly suggests a causal relationship (e.g., reaction after withdrawal and re-administration).
Not evaluable	There is insufficient information to determine the causality between the event and the investigational product. The investigator may change her/his causality assessment based on subsequent follow-up information and modify the appropriate AE/SAE report.

11.1.5 Adverse Events Based on Symptoms and Signs

All AEs spontaneously reported by patients or healthcare professionals (open questions from the study personnel: "Have you had any health problems since your last visit/since last inquiry"), or the AEs identified by observation will be collected and recorded in the eCRF.

11.1.6 Adverse Events Based on Examinations and Testing

Protocol-specified laboratory tests and test results, i.e., vital signs, ECGs, and other safety assessments, will be summarized in the clinical study report. If these parameters suggest abnormalities compared with baseline, they will be reported as AEs only if criteria for SAEs are met, or they are clinically significant judged by the investigator, or they lead to discontinuation of study treatment (except those due to disease progression).

When abnormalities in laboratory test values, vital signs, ECGs, or other safety assessments are reported as AEs, the investigator should use clinical terms rather than laboratory terms whenever possible (e.g., use anemia instead of hemoglobin decreased).

Laboratory abnormalities due to unequivocal disease progression should not be reported as AEs. Any new or worsening clinically relevant abnormality in the physical examination compared to the baseline assessment will be reported as an AE.

11.1.7 Hy's Law

Occurrences of AST or ALT $\geq 3 \times$ ULN and total bilirubin $\geq 2 \times$ ULN may need to be reported as SAEs. Cases that comply with Hy's law require expedited reporting in accordance with regulatory guidelines. At the first time, the investigator should be responsible for determining whether the subject complies with the Hy's law. The detailed information on Hy's Law and treatment measures are provided in [Appendix C](#).

11.1.8 Disease Progression

Disease progression is considered as a worsening of the patient's condition, which can be an increase in the severity of the disease under investigation and/or an increase in the symptoms of the disease.

The development of new lesions in the primary tumor under investigation or progression of existing metastases should be considered as disease progression rather than an AE. Unequivocal disease progression should not be reported as an AE during the study.

11.1.9 Newly Developed Cancer

A new cancer should be considered an SAE and usually meets the criteria for severe disease. Newly developed cancers refer to those cancers that are not the main reason for the study

treatment and are found after the patient has been included in the study. Newly developed cancers do not include metastases of the original cancer.

11.1.10 Handling of Death Cases

All deaths that occur during the study or within the follow-up period after the discontinuation of treatment should be reported as follows:

- Death unequivocally related to disease progression should be reported to the monitor at the monitoring visit and should be recorded in the eCRF, but should not be reported as an SAE during the study.
- If death is not apparently caused by the progression of the disease under investigation, the AE leading to death should be reported as an SAE to the monitor within 24 hours. The report should include an evaluation of disease progression, the main cause of death, and other possible causes of death.
- Death with an unknown cause should be reported as an SAE within 24 hours of awareness of the study site, but every effort should be made to determine the cause of death. Autopsy may help assess the cause of death. If an autopsy is performed, a copy of the autopsy results should be reported to the Sponsor within 24 hours after the results are issued.

11.1.11 Reporting of Adverse Events

All SAEs must be reported regardless of the causality to investigational product or study procedures. All SAEs will be recorded in the eCRF. Any SAE occurring throughout the study (from informed consent to the end of the follow-up period) should be notified the Sponsor promptly by the investigator or other site personnel no later than 24 hours after becoming aware of the SAE. Contact information is shown in Table 6.

Table 6 Contact Information for Adverse Event Reporting

Name	Responsibility in the study	Address and telephone number
[name]	Safety Physician for AE/SAE Reporting, Sponsor Study Team 24-hour Emergency Contact	[name] Mobile: [name] Fax: [name] E-mail: [contact]

The designated Sponsor's representative works with the investigator to ensure that all necessary information is recorded in the Sponsor's secure data entry system: fatal and life-threatening events are recorded within 1 calendar day of initial notification; and all other SAEs are recorded within 5 calendar days of initial notification.

For fatal or life-threatening AEs with missing important or relevant information, proactive actions will be taken immediately. The investigator or other personnel at the study site should promptly notify the Sponsor of any subsequent information of a previously reported SAE, no later than 24 hours after awareness of the subsequent information.

11.2 Overdose

The investigator should closely monitor any subject who receives a higher dose of the study drug than expected and should provide appropriate supportive care and close follow-up. Overdose should be recorded as follows:

- AEs or symptoms associated with overdose should be recorded in both the AE and overdose sections of the eCRF.
- Overdose without relevant symptoms will be recorded only in the overdose section of the eCRF, i.e., the overdose without discomfort is not considered an AE per se and does not need to be recorded in the AE section of the eCRF.

If an overdose occurs during the study, the investigator or other personnel at the study center should notify the Sponsor promptly or within 24 hours of awareness of the event. The designated Sponsor's representative will work with the investigator to ensure that all necessary information is recorded in the Sponsor's secure data entry system.

SAEs related to overdose will be reported according to the procedure for SAE reporting. Other cases must be reported within 30 days of occurrence.

11.3 Pregnancy Report

All cases of pregnancy and related outcomes during the clinical study (from the first treatment until 28 days after discontinuation of treatment) should be reported to the Sponsor.

11.3.1 Pregnancy of Female Subjects

If a female subject becomes pregnant, she should immediately discontinue study treatment, and the investigator must report the pregnancy to the Sponsor within 24 hours of awareness. The investigator should follow up the pregnancy outcome until 28 days after delivery, and report the outcome to the Sponsor.

Pregnancy itself is not considered as an AE unless any negative pregnancy outcome, such as stillbirth, spontaneous abortion and fetal malformation, is considered as an SAE, and should be

reported within specified time limit for SAE reporting. Selective abortion without complications is not considered as an AE.

The designated Sponsor's representative works with the investigator to ensure that all necessary information is recorded in the Sponsor's secure data entry system: SAEs are recorded within 1 calendar day or 5 calendar days of initial notification; and other cases are recorded within 30 calendar days of initial notification.

11.3.2 Pregnancy of Partners of Male Subjects

If the partner of a male subject becomes pregnant during the clinical study, the subject will continue the clinical study, and the investigator must report it to the Sponsor within 24 hours of awareness of the pregnancy of the subject's partner.

Pregnancy of the partner of a male subject is not considered an AE. The investigator should follow up the pregnancy outcome of his partner until 28 days after delivery, and report the outcome to the Sponsor. Any negative pregnancy outcome, such as stillbirth, spontaneous abortion and fetal malformation, is considered as an SAE, and should be reported within specified time limit for SAE reporting.

Information regarding pregnancy should not be collected from male subjects, but should be collected from their partners with the partner's informed consent.

11.4 Recommended Management for Toxicity

11.4.1 Dose Reduction

During toxicity management, the dose of the investigational product can be reduced according to the doses specified in Table 7 below. After dose reduction, it cannot be adjusted back to the higher dose level. If the dose for a patient has been reduced to the lowest level but is still intolerable, withdrawal from the study will be recommended.

Table 7 Dose Reduction Rules for Study Drug

HS-10296 group		
	Initial treatment	Dose reduction treatment
Dose	110 mg/d HS-10296	55 mg/d HS-10296
Drug	HS-10296 active drug, 55 mg/tablet, 2 tablets Gefitinib placebo tablets (placebo 250 mg), 1 tablet	HS-10296 active drug, 55 mg/tablet, 1 tablet HS-10296 placebo tablets (placebo 55 mg), 1 tablet Gefitinib placebo tablets (placebo 250 mg), 1 tablet
Usage	Once daily, orally	Once daily, orally
Gefitinib group		
	Initial treatment	Dose reduction treatment
Dose	250 mg/d gefitinib	No dose reduction, treated at the same dose
Drug	Gefitinib active drug, 250 mg/tablet, 1 tablet HS-10296 placebo tablets (placebo 55 mg), 2 tablets	No dose reduction, treated at the same dose
Usage	Once daily, orally	Once daily, orally

11.4.2 Dose Modifications Associated with Adverse Events

If a subject experiences CTCAE Grade 3 or higher and/or other unacceptable toxicity (any grade) judged by the investigator that cannot be attributed to disease or disease-related progression, and that is related to the dose of the investigational product judged by the investigator, the dose will be interrupted and supportive care will be administered as needed according to local practice/guidelines.

If the toxicity recovers to \leq CTCAE Grade 1 or to baseline (whichever is met first) within 2 weeks of onset, the normal dose or reduced dose of the investigational product as shown in Table 7 may be resumed. If the normal dose is resumed, the subject should be closely monitored for 3 days, and if the same toxic effect occurs within the 3 days, a dose reduction should be considered. The above decision requires agreement between the investigator and the Sponsor's physician.

If the toxicity does not recover to \leq CTCAE Grade 1 or to baseline within 2 weeks of onset, the subject should withdraw from the study and follow-up should be continued until recovery of the toxicity. Individual-specific dose modifications other than those shown in Table 7 will not be allowed.

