In view of the above-mentioned adverse event profiles, the following regulations are set forth in the protocol to minimize the risk: 1) The design of safety indicators has covered the common adverse reactions of similar drugs, changes that required close monitoring suggested in completed preclinical and clinical studies of HS-10296, as well as the observation of the toxicity of important organs such as heart and lungs. Discontinuation criteria for subjects and clinical trials will be specified in the protocol. 2) This study will be conducted in a medical institution with clinical study qualification, and experienced investigators will be selected to conduct the clinical studies. 3) During the conduct and implementation of the study, physicians with rich experience in clinical practice will regularly monitor and check the health status of patients, and promptly take corresponding treatment measures in the event of abnormal changes. 4) In addition to completing the safety examinations at the time points specified in the protocol, the adverse events occurring outside the hospital will be monitored via patient's diary, telephone or in-hospital follow-up. 5) Additional tests can be performed at any time if it is deemed necessary by the investigator. After the start of the study, in case of a special event, the Ethics Committee and National Medical Products Administration may immediately terminate the study when necessary.

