7.5 Blinding

From the start of randomization until disease progression as assessed by the investigator per

RECIST 1.1, the information of the actual treatments will remain blinded to the subjects, the investigator, data analysts, the Sponsor, and all medical personnel involved in the treatment or clinical assessments.

Randomization numbers and study drug numbers will be obtained via the IWRS. The blinded control of the drug uses a double dummy technique. The packaging, mode of administration, labeling, appearance, taste and odor of HS-10296 tablets and HS-10296 placebo tablets (and gefitinib tablets and gefitinib placebo tablets) will be exactly the same to conceal the true information of the treatment drug. HS-10296 tablets and gefitinib placebo tablets will be packaged together. Gefitinib tablets and HS-10296 placebo tablets will also be packaged together. Drugs will be numbered after the combined packaging. The blinding code will be stored in the IWRS system and at the administrator for randomization.

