8.1.2 Dosage Form, Manufacturing, Packaging and Labeling

In this protocol, the investigational product will be provided to each study site after being uniformly packaged and numbered. The labeling of the drug will include, but not limited to the

following information: protocol number, investigational product number, batch number, strength, quantity of dosage units, instructions for use, storage conditions, country-specific regulatory warning statements, and name and address of the Sponsor.

HS-10296 tablets will be provided by Jiangsu Hansoh Pharmaceutical Group Co., Ltd. Gefitinib tablets are commercially packaged. The products should be stored according to package insert. All placebo tablets will be manufactured by Jiangsu Hansoh Pharmaceutical Group Co., Ltd. with the same appearance as that of the active drug of the strength used.

In this study, 3 types of drug packaging kits need to be prepared and classified as normal medication kit for the test group (HS-10296 group), normal medication kit for the control group (gefitinib group), and dose reduction kit for the test group (HS-10296 group). Each kit will contain the drugs required between two adjacent dispensing intervals, and the number of each small package in the kit will be calculated according to the dispensing cycle. There will be a single dose of active drug and placebo tablets (total of 3 tablets) in each small package, and only one small package in the kit will be required for once daily dosing. All remaining drugs and packages should be recovered after the end of the study.

During the study, the investigational product will be provided according to the Table 2.

Table 2 Investigational Product

Normal medication			
Package	Investigational Product	Small package (per dosage)	Manufacturer
Normal medication kit for the test group	HS-10296 tablets	55 mg/tablet (2 tablets)	Jiangsu Hansoh Pharmaceutical Group Co., Ltd.
	Gefitinib placebo tablets	Placebo 250 mg (1 tablet)	Jiangsu Hansoh Pharmaceutical Group Co., Ltd.
Normal medication kit for the control group	Gefitinib tablets	250 mg/tablet (1 tablet)	AstraZeneca Pharmaceutical Co., Ltd.
	HS-10296 placebo tablets	Placebo 55 mg (2 tablets)	Jiangsu Hansoh Pharmaceutical Group Co., Ltd.
Dose reduction			
Package	Investigational Product	Small package (per dosage)	Manufacturer
Dose reduction kit for the test group	HS-10296 tablets	55 mg/tablet (1 tablet)	Jiangsu Hansoh Pharmaceutical Group Co., Ltd.

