9.3 Unscheduled Visits/Examinations

The investigator may schedule unscheduled visits or examinations according to the subject's condition, especially if the subject experiences an AE. Unscheduled visits and unscheduled

examinations performed during that visit will be recorded in the eCRF, along with the reason for the unscheduled visit (or examination).

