10.1.10 Laboratory Tests

Laboratory tests will be performed at screening, every 3 weeks for C1 to C7, every 6 weeks for C7 + cycles, on C1D8 and C1D15, and at discontinuation follow-up as per the study plan ([Appendix B](#)).

Additional tests may be performed if it is deemed necessary by the investigator as appropriate.

The values, units, and reference ranges of the test results should be recorded in the eCRF.

Laboratory results that reach CTCAE (4.0) Grade 3 or have a significant change from baseline and are considered to be of clinical interest will be reexamined/confirmed within 7 days and

followed up accordingly.

Laboratory test items are listed in Table 3.

Table 3 Laboratory Test Items

Clinical Chemistry	Hematology	Urinalysis
Serum (S)/Plasma (P)-albumin	Blood (B) -Hemoglobin	U-Glucose
S/P-ALT	B-White blood cells	U-Protein
S/P-AST	B-Hematocrit	U-Blood
S/P-Alkaline phosphatase	B-Red blood cell count (RBC)	
S/P-Bilirubin, Total bilirubin	B-Absolute differential white blood cell count	
S/P-Calcium, Total blood calcium	Neutrophils	
S/P-Creatinine	Lymphocytes	
S/P-Creatine kinase	Monocytes	
S/P-Glucose	Basophils	
S/P-LDH	Eosinophils	
S/P-HbA1C	B-Platelet count	
S/P-Magnesium	B-Reticulocytes	
S/P-Potassium		
S/P-Sodium		
S/P-Urea nitrogen or urea (either)		

If AST or ALT $\geq 3 \times$ ULN and total bilirubin $\geq 2 \times$ ULN, please refer to [Appendix C](#) (Hy's law) for further guidance for actions to be taken in the event of combined increases in aminotransferases and total bilirubin.

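### After a toxicity or QTcF hold, the 3-day check is tied to resuming the normal dose, so it is not prompted for a gefitinib patient restarted on a blinded 'reduced' order, who is back on 250 mg

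*Protocol*

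**What the plan says.** Protocol 11.4.2 covers holds for Grade 3 or higher, or otherwise unacceptable, dose-related toxicity. Protocol 11.4.5 covers holds for QTcF prolongation. In both, if the event recovers to Grade 1 or to baseline within 2 weeks, either the normal or the reduced Table 7 dose may be restarted, by agreement between the investigator and the Sponsor's physician. Both sections then use the same words: "If the normal dose is resumed, the subject should be closely monitored for 3 days". If the toxicity returns in that time, a reduction is to be considered. Neither section gives a matching instruction for a restart at the reduced level.

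For gefitinib, Table 1 (8.1.1) and Table 7 (11.4.1) both define the reduction as "No dose reduction, treated at the same dose". Section 8.1.2 lists three kit types, and the only one that lowers a dose is the "dose reduction kit for the test group (HS-10296 group"). Section 7.5 states that, until investigator-assessed progression, "the information of the actual treatments will remain blinded to the subjects, the investigator, data analysts, the Sponsor" and the treating and assessing staff.

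Other provisions bear on the same period:
- **4.3.1:** "the adverse events occurring outside the hospital will be monitored via patient's diary, telephone or in-hospital follow-up".
- **9.3:** unscheduled visits are allowed, "especially if the subject experiences an AE".
- **10.1.10:** Grade 3 laboratory values "will be reexamined/confirmed within 7 days".
- **10.1.13:** eye symptoms lead to an examination within 48 hours.
- **11.4.5:** during a QTcF event, ECGs are monitored routinely until return to baseline.
- **11.4.1:** for a patient "reduced to the lowest level but is still intolerable, withdrawal from the study will be recommended".

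**The concern.** The check is triggered by the dose level resumed, but the people who must act on it see only the level ordered. In the HS-10296 arm the two agree. In the gefitinib arm they do not: a reduced order leaves the full 250 mg in place. A patient who has just recovered from Grade 3 toxicity or marked QTcF prolongation can therefore return to the full dose that was held, while blinded staff have reason to believe that the dose may have been lowered.

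What is at stake is early detection of recurrence in that patient. It matters even though Table 7 offers no further step down, because recurrence after a reduced order still calls for a decision: a new hold, permanent discontinuation or withdrawal.

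**Working it through.** There is no planned figure to reproduce. The check sets the restart rule against the dosing tables.

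**Step 1. Dose after restart.** Inputs: Tables 1 and 7 for the doses; 11.4.2 and 11.4.5 for the trigger. Formula: restart dose / starting dose.

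| Arm | Order | Active dose after restart | Share of starting dose | 3-day check prompted by the order? |
|---|---|---|---|---|
| HS-10296 | normal | 110 mg | 110/110 = 100% | yes |
| HS-10296 | reduced | 55 mg | 55/110 = 50% | no |
| Gefitinib | normal | 250 mg | 250/250 = 100% | yes |
| Gefitinib | reduced | 250 mg | 250/250 = 100% | no |

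Three of the four combinations resume the full dose, and the check is prompted in two of those three. That the dose stays at 250 mg is stated in the tables. What the IWRS dispenses for such an order is my inference from the three kit types.

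**Step 2. Can the rule be applied by actual dose?** That requires knowing the arm. The two parties who agree the restart are both blinded under 7.5, and no text assigns the IWRS or an unblinded person to start the check.

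**Step 3. The QTcF case.** Section 11.4.5 allows restart at Grade 1 or baseline, whichever comes first, but ECG monitoring runs to baseline. The two stopping points differ:
- Restarted at Grade 1, not yet at baseline: ECG monitoring continues after restart, whatever level was ordered.
- Restarted at baseline: that monitoring has ended, and a reduced order prompts nothing further.

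Section 11.4.2 has no equivalent sentence, so Step 3 does not narrow the general toxicity case.

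**Step 4. Next fixed safety visit.** Scheduled days in Appendix B, by cycle: 1, 8, 15, 22, 43, 64, 85, 106, 127.
- Within C1: 8 − 1 = 15 − 8 = 22 − 15 = 7 days.
- From C2 to C7: 43 − 22 = 21 days, and 21 days for each later step to day 127.
- After C7: 2 cycles × 21 = 42 days, or 6 weeks.
- From C23: either 6 weeks (10.1.6, 10.1.9 to 10.1.11, Appendix B comment a) or 4 × 21 = 84 days, which is 12 weeks (9.1.2.2). The Appendix B column header also gives a 6/12-week pattern. The documents are inconsistent here.

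These are nominal maxima, reached only if the restart falls just after a scheduled visit and there is no contact in between. They show when the next fixed visit falls and do not measure risk.

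**The case against.** **The text says resumed, not ordered.** Read literally, a gefitinib patient on 250 mg has resumed the normal dose and is covered. Blinded staff also have Table 7, know that a reduced order may change nothing, and may choose to monitor every restart. This stands to the extent that the protocol does not exclude these patients. The gap is practical: staff cannot identify them, and nothing asks for the check after every restart.

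**The restriction may be deliberate.** The same sentence links the 3 days to considering a reduction, and after a reduced order Table 7 has no lower step. Limiting the check to the branch with a step left is coherent. It is therefore an inference that the protocol sees full-dose re-exposure in itself as the reason for observation. But recurrence after a reduced order still has consequences under 11.4.1, 11.4.2 and 11.4.5, so early observation is useful there too.

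**Other safeguards apply.** A reader might infer that these patients go unmonitored. The documents do not support that, given diary, telephone or in-hospital follow-up, unscheduled visits, laboratory re-tests and eye examinations. These are, however, general, optional or dependent on a finding or symptom. None recommends early observation because treatment was restarted. A reader might also infer that QTcF patients have no ECG monitoring after a reduced-order restart; Step 3 shows that this fails for those restarted at Grade 1 and not yet at baseline.

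**It is only a recommendation.** That is correct: the section is headed as recommended management and uses 'should'. This keeps the weight low.

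**Conclusion.** The point holds as a minor gap in safety wording and is worth closing because the change is cheap. One of the three combinations that return to full dose is not prompted for the 3-day check. For general toxicity it affects any gefitinib patient restarted on a reduced order; for QTcF it is confined to those restarted at baseline.

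The conclusion rests on blinding being intact at restart and on staff acting on the order they gave. It concerns the randomized blinded treatment, not the open-label crossover. The number of patients affected is not given, and what close monitoring consists of is not defined, so no risk can be computed.

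A reader might infer a bias in the treatment comparison or a threat to the trial's conclusions. The documents give no basis for either: the rule does not enter the PFS definition, and alpha and power are unaffected. Nor should the possible 12-week interval be counted as part of this gap; it is a separate inconsistency in the visit schedule.

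**What to change.** In 11.4.2 and 11.4.5, replace the opening condition with *After every restart, whichever dose level is ordered*, keep the 3-day instruction as it stands, and end the sentence there. Put the recurrence step in its own sentence, limited to normal-dose orders, so that a reduction is still considered in that branch. Leave recurrence after a reduced order to the existing rules: a new hold or permanent discontinuation under 11.4.2 and 11.4.5, and recommended withdrawal under 11.4.1.

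The wording is the same in both arms, so it reveals nothing about allocation. The check would then be recommended in all four combinations and so in three of three full-dose restarts. The cost is one sentence changed in each of two sections and a site memo, with no new kit and no unblinding. The downside is extra contacts for HS-10296 patients truly reduced to 55 mg; the documents do not give their number.
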